9.2 Treatment Period

9.2.1 Week 1 (Visit 3)

The Week 1 Visit (Visit 3) will take place 7 days \pm 3 days after the Baseline Visit. The following procedures will be performed at Visit 3:

- Perform an accountability check on any remaining study drug as well as empty study drug bottles.
- Record any AEs that have occurred since the previous visit and any changes in concomitant medications.
- Complete CGAS.
- Complete C-SSRS.
- Complete global COVID-19 impact assessment.
- Record vital signs (blood pressure, pulse rate, temperature, and respiration rate).

When all of these procedures have been performed, the study drug will be dispensed and the next visit scheduled.

CONFIDENTIAL

Refer to [Section 8.1.3](#) for assessments if Visit 3 is done remotely. Study drug will be delivered to subjects via curbside (preferred) or courier.

9.2.2 Week 2 (Visit 4)

The Week 2 Visit (Visit 4) will take place 14 days \pm 3 days after the Baseline Visit. The following procedures will be performed at Visit 4:

- Perform an accountability check on any remaining study drug as well as empty study drug bottles.
- Record any AEs that have occurred since the previous visit and any changes in concomitant medications.
- Complete CGAS, PARS, and CGI-S.
- Complete C-SSRS.
- Complete global COVID-19 impact assessment.
- Record vital signs (blood pressure, pulse rate, temperature, and respiration rate).
- Assess the subject for dose escalation: subjects who can tolerate the current dose may have a dose escalation at the investigator's discretion, taking into account the CGI-S score.

When all of these procedures have been performed, and the dose has been confirmed, the study drug will be dispensed and the next visit scheduled. Subjects receiving study drug in the morning will be instructed to withhold taking the morning dose on the day of the Week 4 Visit (Visit 5) and to bring their study drug to the visit.

Refer to [Section 8.1.3](#) for assessments if Visit 4 is done remotely. Study drug will be delivered to subjects via curbside (preferred) or courier.

9.2.3 Week 4 (Visit 5)

The Week 4 Visit (Visit 5) will take place 4 weeks \pm 3 days after the Baseline Visit. The following procedures will be performed at Visit 5:

- Perform an accountability check on any remaining study drug as well as empty study drug bottles.
- Record any AEs that have occurred since the previous visit and any changes in concomitant medications.
- Complete CGAS.
- Complete C-SSRS.
- Complete global COVID-19 impact assessment.
- Record vital signs (blood pressure, pulse rate, temperature, respiration rate, height, and weight).
- Record BMI.
- Subjects on morning dosing:

CONFIDENTIAL

- Collect a predose PK blood sample.
- Administer study drug.
- Collect a PK blood sample at \geq 1 hour postdose.
- Subjects on evening dosing:
 - Collect 2 PK blood samples at random times during the visit (ie, postdose from the dose received the previous evening), at least 2 hours apart from each other.
- Assess the subject for dose escalation: subjects who can tolerate the current dose may have a dose escalation at the investigator's discretion, taking into account the CGI-S score.

When all of these procedures have been performed, the study drug will be dispensed and the next visit scheduled.

Refer to [Section 8.1.3](#) for assessments and to [Table 1](#) for assessment windows if Visit 5 is done remotely. Study drug will be delivered to subjects via curbside (preferred) or courier.

9.2.4 Week 6 (Visit 6)

The Week 6 Visit (Visit 6) will take place 6 weeks \pm 3 days after the Baseline Visit. The following procedures will be performed at Visit 6:

- Perform an accountability check on any remaining study drug as well as empty study drug bottles.
- Record any AEs that have occurred since the previous visit and any changes in concomitant medications.
- Complete CGAS.
- Complete C-SSRS.
- Complete global COVID-19 impact assessment.
- Record vital signs (blood pressure, pulse rate, temperature, and respiration rate).

When all of these procedures have been performed, the study drug will be dispensed and the next visit scheduled.

Refer to [Section 8.1.3](#) for assessments if Visit 6 is done remotely. Study drug will be delivered to subjects via curbside (preferred) or courier.

9.2.5 Week 8 End of Treatment or Early Withdrawal (Visit 7)

The Week 8 End of Treatment or Early Withdrawal Visit (Visit 7) will take place 8 weeks \pm 3 days after the Baseline Visit or at early withdrawal. The following procedures will be performed at Visit 7:

CONFIDENTIAL

- Perform an accountability check on any remaining study drug as well as empty study drug bottles.
- Record any AEs that have occurred since the previous visit and any changes in concomitant medications.
- Complete CGAS, PARS, and CGI-S.
- Complete C-SSRS.
- Complete global COVID-19 impact assessment.
- Record vital signs (blood pressure, pulse rate, temperature, respiration rate, height, and weight).
- Record BMI.
- Record any changes from baseline in physical examination.
- Perform an ECG.
- Collect samples for hematology, clinical chemistry including thyroid, and urinalysis tests.
- Collect urine sample for drug screening (alcohol, opioids, benzodiazepines, tetrahydrocannabinol, barbiturates, and amphetamines).
- Perform a urine pregnancy test, if applicable.
- Collect 2 PK blood samples at random times during the visit (ie, postdose from the dose received in the morning or the previous evening), at least 2 hours apart from each other.

When all of these procedures have been performed, the study drug for the down taper period will be dispensed and the next visit scheduled.

Refer to [Section 8.1.3](#) for assessments and to [Table 1](#) for assessment windows if Visit 7 is done remotely. Study drug will be delivered to subjects via curbside (preferred) or courier. All attempts should be made to collect safety labs within 6 weeks of the Visit 7 date.

9.3 Down Taper Period

9.3.1 Week 9 (Visit 8)

The Week 9 Visit (Visit 8) will take place 9 weeks \pm 3 days after the Baseline Visit. The following procedures will be performed at Visit 8:

- Perform an accountability check on any remaining study drug as well as empty study drug bottles.
- Record any AEs that have occurred since the last visit and any changes in concomitant medications.
- Complete C-SSRS.
- Record vital signs (blood pressure, pulse rate, temperature, and respiration rate).
- Schedule a follow-up telephone contact in 1 week's time.

CONFIDENTIAL

Refer to [Section 8.1.3](#) for assessments and to [Table 1](#) for assessment windows if Visit 8 is done remotely.

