8 INVESTIGATIONAL PLAN

8.1 Overall Study Design and Plan: Description

This is a randomized, multicenter, double-blind, flexibly-dosed, placebo-controlled parallel group study of escitalopram in the treatment of children (aged 7 through 11 years) and adolescents (aged 12 through 17 years) with GAD.

The study design incorporates an up to 3-week screening period, an 8-week double-blind, acute treatment period, and a 1-week double-blind down taper period.

Approximately 430 subjects will be screened and a total of approximately 256 subjects are planned to be randomized in a 1:1 ratio to either escitalopram or placebo. The randomization schedule will be stratified by age at randomization (grouped as 7-11 years vs. 12-17 years) and sex, and blocked.

Subjects will begin with a 10 mg/day dose of escitalopram (taken orally) or matching placebo for the first 2 weeks of double-blind treatment. At the end of Week 2, subjects who can tolerate the current dose of 10 mg/day may have a dose escalation to 20 mg/day of escitalopram or matching placebo. Dose escalation will be at the investigator's discretion taking into account the Clinical Global Impression of Severity (CGI-S) score. Subjects who remain on the 10 mg/day dose of escitalopram or matching placebo will be evaluated again at Week 4 for a possible dose escalation to 20 mg/day at the investigator's discretion. Dose escalations cannot be made at any other time during the study. The dose may be decreased from 20 mg/day to 10 mg/day following discussion with the medical director if the subject does not tolerate the 20 mg/day dose. At the end of the treatment period or at early withdrawal, subjects will enter a 1-week double-blind down taper period with a follow-up telephone contact 1 week after the end of the double-blind down taper period.

A blinded interim analysis will be conducted when 75% of randomized subjects have either completed or discontinued the study in order to check the assumptions in the sample size calculation. Based on this, the sample size may be increased to ensure an adequate power. However, due to the difficulties in recruiting pediatric subjects with GAD, the number of subjects in each treatment arm will be capped at 160.

The study design is shown in [Figure 1](#).

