8.3.5 Removal of Subjects From the Study

A subject may voluntarily withdraw or be withdrawn from the study at any time for reasons including, but not limited to, the following:

- Withdrawal of consent
- Use of non-permitted concurrent therapy
- Noncompliance with the study drug or study schedule
- Lost to follow-up
- Adverse event
- Investigator request
- Intercurrent illness
- Protocol deviation
- Pregnancy
- Sponsor request
- Lack of efficacy
- Due to the COVID-19 pandemic
- Death

Subjects who do not complete the study will not be replaced.

Subjects are free to withdraw from the study at any time without providing reason(s) for withdrawal and without prejudice to further treatment. The reason(s) for withdrawal will be documented in the electronic case report form (eCRF).

Subjects withdrawing from the study will be encouraged to complete the same final evaluations as subjects completing the study according to this protocol, particularly

CONFIDENTIAL

safety evaluations. The aim is to record data in the same way as for subjects who completed the study.

Subjects who withdraw early from the study should complete the End of Treatment Visit and enter the 1-week down taper period.

Subjects should be monitored for the following symptoms when discontinuing treatment: dysphoric mood, irritability, agitation, dizziness, sensory disturbances (eg, paresthesias such as electric shock sensations), anxiety, confusion, headache, lethargy, emotional lability, insomnia, and hypomania. A gradual reduction in dose rather than abrupt cessation is recommended, whenever possible.

Reasonable efforts will be made to contact subjects who are lost to follow-up (eg, 3 attempts to contact the subject by telephone/letter). These efforts must be documented in the subject's file.

The sponsor has the right to terminate the study at any time in case of serious adverse events (SAEs) or if special circumstances concerning the investigational product or the company itself occur, making further treatment of subjects impossible. In this event, the investigator(s) will be informed of the reason for study termination.

Pregnancy

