8.4 Investigational Products

8.4.1 Investigational Products Administered

Subjects randomized to the escitalopram arm will receive escitalopram 10 mg/day for the first 2 weeks. At the end of Week 2, subjects who can tolerate the current dose of 10 mg/day may have a dose escalation to 20 mg/day. Dose escalation will be at the

CONFIDENTIAL

investigator's discretion taking into account the CGI-S score. Subjects who remain on 10 mg/day will be evaluated again at Week 4 for a possible dose escalation to 20 mg/day at the investigator's discretion. Dose escalations cannot be made at any other time during the study. The dose may be decreased from 20 mg/day to 10 mg/day following discussion with the medical director if the subject does not tolerate the 20 mg/day dose.

At the end of the 8-week double-blind acute treatment period, or at withdrawal, the subject will enter a 1-week double-blind down taper period.

For subjects receiving escitalopram 10 mg/day, the doses given during the double-blind down taper period will be as follows:

- Week 9: Subjects will receive placebo.

For subjects receiving escitalopram 20 mg/day, the doses given during the double-blind down taper period will be as follows:

- Week 9: Subjects will receive 10 mg/day.

Subjects randomized to the placebo arm will receive matching placebo during the double-blind treatment period. Subjects will be evaluated at the end of Week 2 and Week 4 and subjects tolerating 10 mg/day matching placebo may be indicated for dose escalation by the investigator but in a blinded fashion will continue to receive matching placebo. Subjects receiving placebo will follow a similar down tapering schedule at the end of the double-blind treatment period.

For details on overdose of escitalopram, please see [Section 10.1.2.2.5](#).

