9.4 Follow-up

9.4.1 Week 10 (Follow-up Telephone Contact)

The follow-up telephone contact to review subject safety will take place at Week 10 (10 weeks \pm 3 days after the Baseline Visit).

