For subjects receiving escitalopram 20 mg/day, the doses given during the double-blind down taper period will be as follows:

Week 9: Subjects will receive 10 mg/day.

AbbVie Escitalopram

SAP SCT-MD-60 Allergan

Page 9 of 53

Subjects randomized to the placebo arm will receive matching placebo during the double-blind acute treatment period. Subjects evaluated at the end of Week 2 and Week 4 and tolerating 10 mg/day matching placebo may be indicated for dose escalation by the investigator but in a blinded fashion will continue to receive matching placebo. Subjects receiving placebo will follow a similar down tapering schedule at the end of the double-blind acute treatment period.

A follow-up telephone contact will take place 1 week after the end of the double-blind down taper period.

[figure not shown]
A blinded interim analysis will be conducted when 75% of randomized subjects have either completed or discontinued the study in order to check the assumptions in the sample size calculation. Based on this, the sample size may be increased to ensure an adequate power. However, due to the difficulties in recruiting pediatric subjects with GAD, the number of subjects in each treatment arm will be capped at 160.

The study design is shown in Figure 1.

Page 10 of 53

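### Visit 8 and the follow-up call are timed from Baseline with no early-withdrawal alternative; read literally, the end-of-taper C-SSRS and vital signs come 14 to 49 days after the taper (minor inconsistency)

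*Protocol*

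**What the plan says.** Two Protocol sentences set the timing. Section 9.3.1 places Visit 8 at 9 weeks ± 3 "days after the Baseline Visit. The following procedures will be performed at Visit 8". Section 9.4.1 reads "The follow-up telephone contact to review subject safety will take place at Week 10 (10 weeks" ± 3 days after Baseline). Neither has an early-withdrawal clause. Section 9.2.5, just before them, does have one: Visit 7 takes place at 8 weeks or at early withdrawal.

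The taper itself follows withdrawal. Section 8.3.5 states: "Subjects who withdraw early from the study should complete the End of Treatment Visit and enter the 1-week down taper period". Section 8.4.1 agrees: "At the end of the 8-week double-blind acute treatment period, or at withdrawal, the subject will enter a 1-week double-blind down taper period".

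The call has a second, different anchor. Section 8.1 ends the taper description "with a follow-up telephone contact 1 week after the end of the double-blind down taper period", and SAP Section 3.0 repeats it: "A follow-up telephone contact will take place 1 week after the end of the double-blind down taper period". The Visit 8 list in 9.3.1 also asks sites to book the call for one week later, but that runs from a Visit 8 that is itself tied to Baseline.

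SAP Table 16.1-2 assigns a Week 9 assessment only if it falls within the down-taper period.

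**The concern.** A subject who withdraws early takes the taper straight away, but 9.3.1 still points to the ninth week after Baseline. Followed literally, the visit meant to close the taper happens after the taper is over. The two rules for the call then give different dates, and for most early withdrawals the Section 8.1 call date comes before Visit 8.

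This matters because, in the schedule of assessments, Visit 8 holds the only scheduled C-SSRS and vital signs after ET. The drug is an SSRI given to children and adolescents, early withdrawals include subjects who leave because of adverse events, and Section 10.1.2.2.4 asks for particular vigilance when the dose changes. The C-SSRS is also summarised separately for the taper period (Protocol 11.6.1.5, SAP 10.5), and a late Visit 8 would not belong to that period.

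**Working it through.** **Inputs** (days counted from Baseline = 0):
- Visit 8: 9 weeks = Day 63, window Day 60 to 66 (9.3.1).
- Call: 10 weeks = Day 70, window Day 67 to 73 (9.4.1).
- Taper: 7 days from ET (8.1, 8.3.5, 8.4.1), so it ends at ET + 7.
- Call under 8.1 and SAP 3.0: end of taper + 7 = ET + 14.
- Scheduled visits at Weeks 1, 2, 4 and 6 = Days 7, 14, 28 and 42.
- Dropout 14% (11.9); 256 planned subjects; cap of 160 per arm (11.8).

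**Completers.** ET at Day 56, taper ends 56 + 7 = 63, gap to Visit 8 = 63 − 63 = 0, call at 63 + 7 = 70. The plan's Week 9 and Week 10 are reproduced, and the two rules agree.

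**Early withdrawals.**
- End of taper to Visit 8: 63 − (ET + 7) = 56 − ET. Over the ± 3-day window, 53 − ET to 59 − ET.
- Delay of the 9.4.1 call against the 8.1 call: 70 − (ET + 14) = 56 − ET.
- End of taper to the 9.4.1 call: 70 − (ET + 7) = 63 − ET.

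| ET | Taper ends (day) | Taper end to Visit 8, days (range) | 8.1 call (day) | 9.4.1 call later by (days) | Taper end to 9.4.1 call (days) |
|---|---|---|---|---|---|
| Week 1 (Day 7) | 14 | 49 (46 to 52) | 21 | 49 | 56 |
| Week 2 (Day 14) | 21 | 42 (39 to 45) | 28 | 42 | 49 |
| Week 4 (Day 28) | 35 | 28 (25 to 31) | 42 | 28 | 35 |
| Week 6 (Day 42) | 49 | 14 (11 to 17) | 56 | 14 | 21 |

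Withdrawal between scheduled visits gives intermediate values; at Week 7 (Day 49) the gap is 56 − 49 = 7 days.

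**Order of contacts.** The 8.1 call precedes nominal Visit 8 when ET + 14 < 63, that is, ET before Day 49 (Week 7).

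**Can the windows absorb it?** The latest date within ET + 1 week ± 3 days is ET + 10. It reaches Day 60, the start of the 9.3.1 window, only if ET ≥ 50. For ET before Day 50 no date satisfies both.

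**Against the 30-day adverse-event window** (10.1.2.2), taking the last dose as the end of a full taper: Visit 8 falls beyond 30 days for ET at Weeks 1 and 2 (49 and 42 days), and the call does so for Weeks 1, 2 and 4 (56, 49 and 35 days).

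**Subjects.** 0.14 × 256 = 35.8, about 36; at the cap, 0.14 × 320 = 44.8, about 45. These are planning figures for all dropouts, not a count of those affected. They include subjects lost to follow-up, who would have no Visit 8, and subjects leaving at Week 7 or later.

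**The case against.** The strongest reply is that the intended timing can be read from the rest of the documents. Section 8.4.1 labels the taper week as Week 9 whenever it occurs. Visit 8 sits under the down-taper heading and in that schedule column. Schedule footnote c gives ± 3 days with no Baseline anchor, and the amendment summary shows that the anchor was removed there as a correction. Section 9.2.5 has the next visit booked when taper drug is dispensed. Section 8.3.5 wants withdrawals recorded in the same way as completers. On this view a site would have to follow one sentence and ignore several others. That stands as evidence of intent and keeps the point minor. It does not correct the text, because 9.3.1 gives the only day count for Visit 8.

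The safety argument is also limited. Section 8.3.5 says "Subjects should be monitored for the following symptoms when discontinuing treatment", and Sections 10.1.2.1 and 10.1.2.2.4 require continuing attention to suicidality. Visit 8 itself asks sites to "Record any AEs that have occurred since the last visit and any changes in concomitant medications". Adverse events are collected to 30 days after the last dose, and unscheduled visits are allowed (9.5). SAP 16.3 uses all post-baseline values for the most severe C-SSRS result and for potentially clinically significant values. All of this stands. Only the timing of one C-SSRS and one set of vital signs is exposed.

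It can also be said that SAP Table 16.1-2 gives no calendar end for the taper period, so a late Visit 8 is outside it only if the period ends at ET + 7. That is an assumption, but it is the plain reading of a 1-week taper. The 7-day late allowance in Section 11.6 adds nothing either way: it runs from the planned visit window, and under a literal 9.3.1 a Week 9 visit is on time.

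**Conclusion.** The inconsistency is real and minor. Sections 9.3.1 and 9.4.1 anchor Visit 8 and the call to Baseline without the early-withdrawal alternative given for Visit 7, and 9.4.1 conflicts with Section 8.1 and SAP Section 3.0. For withdrawals at the scheduled visits from Week 6 back to Week 1, the literal wording puts both contacts 14 to 49 days later than a schedule that follows the taper. This assumes that the taper starts at the ET Visit and lasts 7 days, and that a site applies the written date. The documents do not show how many sites would do so or when dropouts occur, so the number of subjects affected cannot be estimated. The problem lies in those two sentences. The design itself and the primary efficacy analysis are not affected.

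**What to change.** In 9.3.1, time Visit 8 at 1 week ± 3 days after the Week 8/ET Visit. In 9.4.1, time the call at 1 week ± 3 days after the end of the down-taper period, as Section 8.1 already implies. Add one footnote with these anchors to the Week 9 and Week 10 columns of both schedules. The instruction at Visit 8 to book the call a week ahead then works as written, and SAP Table 16.1-2 can stay.

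The cost is a site memo now, or two sentences and a footnote at the next amendment, with no added visit or procedure. Completers stay nominally at Weeks 9 and 10. Because Visit 7 has its own window (Day 53 to 59), their outer limits widen by 3 days each way:
- Visit 8: from Day 60–66 to Day 57–69 (53 + 7 − 3 to 59 + 7 + 3).
- Call: from Day 67–73 to Day 64–76 (53 + 14 − 3 to 59 + 14 + 3).

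If that widening is unwelcome, keep the Baseline timing for completers and add an early-withdrawal alternative to each sentence: 1 week after the Early Withdrawal Visit for Visit 8, and 1 week after the end of the taper for the call.

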9.4 Follow-up

9.4.1 Week 10 (Follow-up Telephone Contact)

The follow-up telephone contact to review subject safety will take place at Week 10 (10 weeks \pm 3 days after the Baseline Visit).

9.5 Unscheduled Visits

Unscheduled visits can be performed if safety concerns arise and at the discretion of the investigator. Additional examinations may be performed as necessary to ensure the safety and well-being of the subjects during the study.

9.6 Duration of Treatment

The duration of treatment will be up to 9 weeks (an 8-week double-blind, acute treatment period, and a 1-week double-blind down taper period).

9.7 End of Study

A subject will have fulfilled the requirements for study completion when the subject has completed all study periods, including the last scheduled follow-up telephone contact at Week 10 as indicated in the Schedule of Assessments in [Section 8.1.2](#).

The end of the study will be the last subject's last scheduled follow-up telephone contact at Week 10 as indicated in the Schedule of Assessments in [Section 8.1.2](#).

10 EFFICACY, SAFETY, AND PHARMACOKINETIC ASSESSMENTS

The planned Schedule of Assessments is in [Section 8.1.2](#).

The modified Schedule of Assessments in conjunction with the COVID-19 pandemic is in [Section 8.1.3](#) and the options for conducting remote visits are outlined in [Section 8.2.2.1](#). For any efficacy or safety assessment data that are collected during a remote visit, the appropriately trained study center staff may conduct the assessment by telephone or videoconference. Sites should remain consistent with the method used for each subject.

CONFIDENTIAL

